7.3.2.5 Follow-up Assessments

Follow-up phone surveys will be conducted by the GHRI Survey Research Program at 2 and 6 months post-enrollment. Each participant will receive a reminder letter and text message approximately one week prior to their interview due date. Professional interviewers will then contact each person by phone to complete the standardized interview.

Persons who are reached by phone but who decline to participate in the full interview will be asked to provide information on each of the main outcomes of interest. Each

person who completes an interview (full or abbreviated) will be mailed a thank you letter and \$30 check or gift card as a thank you for their time.

During each follow-up contact, survey staff will confirm that the contact information on file is correct for each participant (mail address, cell phone number, home number, and email address).

Persons who cannot be reached within 2 weeks of their scheduled due date will be mailed a written survey to complete and return by mail. Persons who are not reached by phone and do not return the written survey within 4 weeks post-due date at 2 month follow-up or 6 weeks post-due date at 6 month follow-up will be coded as unable to reach. Other response options include: refused, deceased, and unknown.

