Mediation Analyses. If the enhanced UC is more effective than UC for either primary outcome at 6 months, we will then conduct mediator analyses to assess whether relevant secondary outcomes measured at 2 months (self-efficacy, motivation, knowledge,) mediate at least part of this effect. Mediation will be explored separately for each significant main outcome. These analyses will be conducted using the framework recommended by Baron and Kenny,⁴⁹ but using more recent statistical methods developed to better quantify and decompose different aspects of the mediation effect.⁵⁰ Having demonstrated the association between the intervention and the outcome variable (the “total effect” of the intervention on the outcome), the second step will be to demonstrate the association between the intervention and each mediator. We will construct a regression model for each mediator with the 2 month score of the mediator as the dependent variable and intervention indicator as independent variables. We will conduct this for each potential mediator and only include those mediators that have at least a $P < 0.10$ -level significant relationship with the intervention as potential mediators in the following step. The third step is to demonstrate the reduction of the intervention effect on the outcome after removing the effect of the mediator(s). We will construct a multi-mediator inverse probability weighted (IPW) regression model. This approach allows us to estimate the direct effect of intervention after rebalancing the intervention groups with respect to the mediators. The application of the IPW approach, as compared to the traditional approach of adjusting for multiple mediators, allows us to more appropriately account for confounding between a mediator and the outcome both

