by additional mediators and by other measured variables. Further, we are better able to estimate the indirect effects of each mediator in a causal framework through decomposition of the total effect of intervention into indirect effects through each mediator and the direct effect after accounting for all mediators. Specifically, we will first model the probability of the intervention given the mediators (all mediators that were found associated with intervention in step 2) using logistic regression adjusting for potential baseline confounders. From this model we will obtain the estimated probabilities that each person received their observed intervention given their observed mediator value. We will then use an IPW regression to model the primary outcomes on intervention status while adjusting for the baseline level of the outcome and mediator and weighting out the effect of the mediator. Comparing the weighted to the unweighted model will allow us to estimate how much of the direct effect of intervention on the outcome can be explained by each potential mediator. We will further be able to quantify the amount of effect explained by each mediator independent of the other mediators.

Process Analyses. Summary statistics will be used to characterize quantitative acceptability ratings and scores. T-tests will be used to compare groups' on continuous ratings and chi-squares for proportions. Open-ended qualitative responses will be reviewed by investigators and may be transcribed and coded thematically, as needed to provide insight into the participants' satisfaction with the intervention programs and their components.

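### The mediation plan promises a separate effect for each mediator, but the weighting it specifies identifies only the combined effect of all retained mediators

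*Combined protocol and SAP*

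**What the plan says.** Section 12.4 runs the mediation analysis only if the enhanced arm does better on a primary outcome at 6 months. The question is whether "secondary outcomes measured at 2 months (self-efficacy, motivation, knowledge,) mediate at least part of this effect". Each candidate is first regressed on arm and kept if P<0.10.

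The next step is a single model: "We will construct a multi-mediator inverse probability weighted (IPW) regression model". Its weights come from a logistic regression that will "model the probability of the intervention given the mediators (all mediators that were found associated with intervention in step 2", with adjustment for baseline confounders. The outcome is then regressed on arm with those weights, adjusting for baseline levels.

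From this the plan expects to "estimate the indirect effects of each mediator in a causal framework". It says that setting the weighted model against the unweighted one shows "how much of the direct effect of intervention on the outcome can be explained by each potential mediator", and it ends with the promise to "quantify the amount of effect explained by each mediator independent of the other mediators".

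On timing, section 7.3.2.5 says: "Follow-up phone surveys will be conducted by the GHRI Survey Research Program at 2 and 6 months post-enrollment". All candidate mediators therefore come from the same 2-month survey.

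**The concern.** A weight built from all retained mediators together removes their influence together. The drop from the unweighted to the weighted estimate belongs to the set, and nothing in it belongs to one score. Dividing it needs something extra: a causal order among knowledge, motivation and self-efficacy, or an assumption that none affects another. Section 12.4 gives no order, no such assumption and no separate weight models. Measurement at one survey supplies no order either.

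Correlation among the scores is a realistic prospect. Section 12.4 justifies weighting partly on the ground that one mediator may confound the relation of another with the outcome. Section 2.2 describes confidence and outcome expectations growing out of the same practice experiences.

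At stake is a reported result. Any published percentage for a single mediator would depend on an analyst's choice that the plan leaves open, while being described as separate from the others and causal.

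There is also a labelling slip. The comparison sentence speaks of explaining the direct effect. The unweighted model estimates the total effect, and the direct effect is what remains after the mediators are accounted for. The same part of section 12.4 uses the terms correctly when it describes decomposing the total effect.

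**Working it through.** **The plan's own figures.** The mediation analysis has no stated sample size, power or effect size. The primary figure does reproduce. For 12% versus 21%, 90% power and two-sided alpha 0.05 with pooled variance, n per arm = [1.960·√(2·0.165·0.835) + 1.282·√(0.12·0.88 + 0.21·0.79)]² / 0.09² ≈ 355.4. This rounds up to 356, or 712 in total. It is not in question here.

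**What the specified comparison yields.** Unweighted estimate = total effect. Weighted estimate = direct effect, given no unmeasured confounding of mediators and outcome. Their difference is the joint indirect effect. One weight model gives one difference per outcome.

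**Assumed inputs (the documents give none).** Three mediators, each raised by a = 0.3 SD by the intervention; equal effects b of each on the outcome; common correlation ρ between the scores given arm and covariates. I use ρ = 0, 0.3 and 0.5.

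**Closed form, linear case.** The joint indirect effect is 3ab whatever ρ is. There are two obvious ways to obtain a figure per mediator:

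- *One at a time* (weight on one score only): ab(1 + 2ρ) each, so the sum divided by the joint effect is 1 + 2ρ.
- *Leave one out* (joint effect minus the effect of the other two): ab(1 − ρ)/(1 + ρ) each, so the sum divided by the joint effect is (1 − ρ)/(1 + ρ).

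| ρ | One at a time, sum ÷ joint | Leave one out, sum ÷ joint |
|---|---|---|
| 0 | 1.0 | 1.0 |
| 0.3 | 1.6 | 0.7/1.3 = 0.54 |
| 0.5 | 2.0 | 0.5/1.5 = 0.33 |

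**Causal order.** If an order is imposed instead, the first mediator carries (1 + 2ρ)/3 of the joint effect and the last (1 − ρ)/[3(1 + ρ)]. The same data then give one mediator 53% or 18% at ρ = 0.3, and 67% or 11% at ρ = 0.5. With two mediators the shares are (1 ± ρ)/2, which is 75% or 25% at ρ = 0.5.

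**Simulation with the weight P(A)/P(A|M)** (binary outcome, risk = 0.14 + 0.02·arm + 0.03·sum of scores, n = 2,000,000):

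- ρ = 0: joint effect 2.7 points. Both methods give about 0.9 points per mediator and sum to 2.7.
- ρ = 0.5: total effect 4.69 points, joint effect 2.68. One at a time gives 1.78 to 1.80 each, sum 5.36 (5.36/2.68 = 2.0). Leave one out gives 0.29 to 0.30 each, sum 0.89 (0.89/2.68 = 0.33).

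At ρ = 0.5 the two methods differ about six-fold for the same mediator. In 1,000 simulated trials of n = 718, the mean single-mediator effect was 1.77 points (SD 0.60) one at a time and 0.29 points (SD 0.27) leave one out. The gap is therefore larger than the sampling spread of either.

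**The case against.** **The text may intend separate weights.** The paragraph lapses into the singular when it describes the weights, refers to each potential mediator, and leans on a cited paper on marginal structural models that is not available here. Terse drafting is a fair reading, and it would be too much to say that the analysts will fit only the joint weight. But no separate weights are specified. If they were fitted, they would be the one-at-a-time version, which overlaps whenever the scores are correlated.

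**The problem is conditional.** It needs a positive primary result and at least two mediators through the screen; three is the maximum. It also concerns correlation left after baseline adjustment, which may be lower than the raw correlation. All of this stands.

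**The numbers are illustrative.** This also stands. Other structures give other ratios. In a pure chain, where arm acts only on the first score and the outcome depends only on the last, each mediator taken singly explains about 100% of the joint effect and the three sum to about 3 times it. Only the lack of a unique split at non-zero correlation is general.

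**A reader might infer that the programme would be refined at the wrong component.** The documents do not support that. Nothing ties a score to a separable programme element. Section 3.1 rests the dissemination decision on effectiveness, and the purchaser tool in section 12.4 uses costs, outcome probabilities and willingness to pay. The mediation hypothesis in section 12.1 is collective and needs no split.

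**Conclusion.** The concern holds in this form: section 12.4 claims a property, a separate effect for each mediator, that the analysis it specifies does not have. The joint indirect effect does not depend on the order of the mediators. The split does, once two or more retained scores are correlated given arm and baseline covariates.

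Under the stated assumptions, single-mediator effects add up to between 0.33 and 2.0 times the joint effect at a residual correlation of 0.5, depending only on method. The discrepancy is nil at zero correlation or with one retained mediator.

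A reader might conclude that the whole mediation analysis fails. It does not: the joint result remains available under the usual assumption of no unmeasured mediator-outcome confounding. The primary analyses and sample size are untouched. This should be corrected before the mediation results are written up, but it is a secondary matter.

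**What to change.** Change the Mediation Analyses text in section 12.4 as follows:

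1. Make the joint indirect effect of the retained mediators the main mediation result. Define it as the unweighted minus the weighted estimate on the risk-difference scale, and report it also as a share of the total effect. Give a bootstrap confidence interval that re-estimates the weights in each resample.
2. Delete the sentence that promises to "quantify the amount of effect explained by each mediator independent of the other mediators".
3. Label any per-mediator results exploratory, overlapping and non-additive. State the weight model used for each and the assumption behind it: a causal order, or no effect of one mediator on another. A range over possible orders would show how far the split depends on that choice.
4. In the sentence comparing the weighted and unweighted models, replace *direct* effect with *total* effect.

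The cost is SAP wording, some bootstrap computing and a narrower mechanistic claim. No new data are needed.

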13 SOURCE DOCUMENTS AND ACCESS TO SOURCE DATA/DOCUMENTS

Study staff will maintain appropriate treatment and research records for this study, in compliance with ICH E6, Section 4.9 and regulatory and institutional requirements for the protection of confidentiality of subjects. Study staff will permit authorized representatives of NIDCR and regulatory agencies to examine (and when required by applicable law, to copy) research records for the purposes of quality assurance reviews, audits, and evaluation of the study safety, progress and data validity.

14 QUALITY CONTROL AND QUALITY ASSURANCE

Alere study staff will be trained on the protocol by Drs. [name], [name], and [name] and/or their proxies, as appropriate to staffs' role on the project (e.g., screening, assessment, intervention delivery). Counselor training will involve a combination of didactic learning and experiential role play until each counselor is adept at delivering the counseling and integrating it with usual care.

Electronic records will be routinely reviewed to ensure quality assurance, including:

- Randomization assignments (blinded) will be monitored to ensure equitable distribution of participants in each arm and to ensure the block stratification scheme is maintained.
- Alere will provide routine reports to GHRI summarizing enrollment metrics including: the number of people invited to be screened for eligibility, the number who are screened eligible, reasons for ineligibility, the number invited to consent, the number who provide consent, the number who complete baseline assessments, and metrics on participation in the counseling calls.
- Alere will send weekly feeds of baseline and screening data to GHRI. Surveys will be periodically checked by the biostatistician or GHRI programmer for missing or out of range values, or other evidence of poor data quality. Systematic errors will be addressed, as appropriate.
- The GHRI biostatistician or programmer will conduct regular screening of follow-up assessment data to identify missing or out of range values, or other evidence of poor data quality. Systematic errors will be addressed, as appropriate.

Phone contacts with quitline callers are routinely recorded by Alere. We will randomly audit at least 10% of these calls for study participants to monitor fidelity to the counseling and may audit other study activities (e.g., screening, consent, and baseline interview) as needed. GHRI fidelity monitors will listen to the randomly sampled calls. GHRI staff will be responsible for auditing and coding compliance with study activities, except that Alere staff may be responsible for auditing fidelity to the usual care counseling. Standardized rating forms will be used to document compliance with study activities, including key elements of the counseling protocol. As needed to address protocol drift, Drs. [name], [name], and [name] will ensure that study staff receive additional supervision and training.

Compliance with the follow-up phone surveys will be audited by supervisors in the GHRI Survey Research Program following standard protocols for fidelity monitoring

15 ETHICS/PROTECTION OF HUMAN SUBJECTS

15.1 Ethical Standard

The investigator will ensure that this study is conducted in full conformity with the principles set forth in The Belmont Report: Ethical Principles and Guidelines for the Protection of Human Subjects of Research, as drafted by the US National Commission for the Protection of Human Subjects of Biomedical and Behavioral Research (April 18, 1979) and codified in 45 CFR Part 46 and/or the ICH E6.

15.2 Institutional Review Board

The protocol, informed consent form(s), recruitment materials, and all subject materials will be submitted to the IRB for review and approval. Approval of both the protocol and the consent form must be obtained before any subject is enrolled. Any amendment to the protocol will require review and approval by the IRB before the changes are implemented in the study.

15.3 Informed Consent Process

With IRB approval, participants will provide verbal consent to participate. Consent will be documented by study staff at Alere Wellbeing and all participants will be mailed written copies of the consent form for their records. Informed consent will include permission to participate in the randomized trial, to have all data collected as part of their quitline counseling program shared with GHRI researchers, and for study staff to contact participants by phone, text or email. Participants will be fully informed of the potential risks and benefits of study participation. Those who decline to consent will still be eligible to participate in the usual care tobacco quitline program. Participants will be informed of their right to withdraw their consent to participate at any time. The consent process will conform to all requirements as set forth by the study IRB.

The consent process will be documented in the study database.

15.4 Exclusion of Women, Minorities, and Children (Special Populations)

Individuals of any gender or racial/ethnic group may participate. Children age 18 to 21 may participate but persons under the age of consent (18 y.o.) will be excluded.

15.5 Subject Confidentiality

Appropriate steps will be taken to safeguard participant confidentiality. This includes the following:

- All study data will be maintained on secure, password protected servers at GHRI and Alere. Only study staff who need this information for their work will have access.

- Electronic data that contains PHI will be transmitted between GHRI and Alere using a secure, HIPPA-compliant FTP site.
- Participants will be identified using subject IDs in all study records.
- We will establish a Business User Agreement with the text messaging vendor, to ensure the confidentiality of study participants is maintained.
- The study protocol, documentation, data and all other identifying information will be held in strict confidence. No information about the study will be released without prior written approval of the sponsor. The study monitor or other authorized representatives of the sponsor may inspect records, as needed.

15.6 Future Use of Identifiable Data

Identifiable information will be destroyed within 5 years of the end of the study, consistent with HIPAA and our IRB requirements.

We have no plans to retain identifiable information beyond this period. If this plan changes, we will obtain appropriate IRB approval and participant consent.

See also Study Records Retention, section 16.5.

16 DATA HANDLING AND RECORD KEEPING

16.1 Data Management Responsibilities

Data collected at Alere Wellbeing and by the GHRI Survey Research Program will be captured in electronic records. Any additional data may be collected on paper and added to electronic records (e.g., mailed survey interview if not able to collect by phone).

If needed, all written source documents will be completed in a neat, legible manner to ensure accurate interpretation of data. When making changes or corrections, staff will cross out the original entry with a single line, and initial and date the change. They will NOT ERASE, OVERWRITE, OR USE CORRECTION FLUID OR TAPE ON THE ORIGINAL SOURCE DOCUMENT.

Final datasets will be saved electronically, clearly labeled and stored in a secure project folder on the GHRI server accessible only to study staff. Data shared between GHRI and Alere Wellbeing will be transferred using a secure FTP site.

No electronic participant data shall be overwritten by study staff. As necessary, variables may be recoded into new variables for analyses, but will be done in a way to preserve the original record. All changes will be documented.

16.2 Data Capture Methods

All data will be captured electronically for this study from either phone surveys (e.g., manual data entry using phone CATI systems), automated intervention records (e.g., Alere system records), or digital audio recordings.

All electronic records will be kept in a 21 CFR Part-11 compliant data capture system, which includes password protection.

16.3 Types of Data

Data for this study will include self-reported survey data (eligibility screening, baseline, and follow-up), electronic data on program utilization (e.g., number of calls completed, duration of behavioral counseling) and program delivery (number of emails and text messages sent), and safety data (e.g., AEs).

16.4 Schedule and Content of Reports

The schedule for data review and reports will be determined by the DSMB during this Board's initial meeting.

16.5 Study Records Retention

All study data will be maintained for at least 5 years after the conclusion of the study. At that time, consistent with HIPAA guidelines, identifying information and linking files will be destroyed unless consent to retain these files is granted by study participants or the IRB.

Following this time, no records will be destroyed without the consent of NIDCR, if applicable. It is the responsibility of the sponsor to inform the investigator when these documents no longer need to be retained

16.6 Protocol Deviations

All staff will immediately report protocol deviations to the GHRI Project Manager, who will inform the PI. Deviations will be considered any noncompliance with this clinical trial protocol, Good Clinical Practice, or the Manual of Procedures. Deviations will be reported in a timely way to the GH IRB. Deviations will also be reported to the NIDCR Program Official via [contact] once monthly.

17 PUBLICATION/DATA SHARING POLICY

This study will comply with the *NIH Public Access Policy*, which ensures that the public has access to the published results of NIH funded research. It requires scientists to submit final peer-reviewed journal manuscripts that arise from NIH funds to the digital archive PubMed Central upon acceptance for publication.

The International Committee of Medical Journal Editors (ICMJE) member journals have adopted a clinical trials registration policy as a condition for publication. The ICMJE defines a clinical trial as any research project that prospectively assigns human subjects to intervention or concurrent comparison or control groups to study the cause-and-effect relationship between a medical intervention and a health outcome. Medical interventions include drugs, surgical procedures, devices, behavioral treatments, process-of-care changes, and the like. Health outcomes include any biomedical or health-related measures obtained in patients or participants, including pharmacokinetic measures and adverse events. The ICMJE policy requires that all clinical trials be registered in a public trials registry such as *ClinicalTrials.gov*, which is sponsored by the National Library of Medicine. Other biomedical journals are considering adopting similar policies. For interventional clinical trials performed under NIDCR grants and cooperative agreements, it is the grantee's responsibility to register the trial in an acceptable registry, so the research results may be considered for publication in ICMJE member journals. The ICMJE does not review specific studies to determine whether registration is necessary; instead, the committee recommends that researchers who have questions about the need to register err on the side of registration or consult the editorial office of the journal in which they wish to publish.

U.S. Public Law 110-85 (Food and Drug Administration Amendments Act of 2007 or FDAAA), Title VIII, Section 801 mandates that a "responsible party" (i.e., the sponsor or designated principal investigator) register and report results of certain "applicable clinical trials:"

NIH grantees must take specific steps to ensure compliance with NIH implementation of FDAAA.

